## 6.3 Premature Termination or Suspension of Study or Investigational Site

#### 6.3.1 Criteria for Premature Termination or Suspension of the Study

The study will be completed as planned unless one or more of the following criteria are satisfied that require temporary suspension or early termination of the study.

- New information or other evaluation regarding the safety or efficacy of the study drug that indicates a significant change in the known risk/benefit profile for the drug, such that the risk is no longer acceptable for subjects participating in the study.
- Significant violation of Good Clinical Practice (GCP) that compromises the ability to achieve the primary study objectives or compromises subject safety.
- Study-specific criteria for terminating the study:
  - a) Subjects in more than 1 cohort have met Cohort Stopping Criteria.
  - b) Any subject in any cohort experiences signs or symptoms of a tremor. (Subjects may not be dosed in this cohort at the same or higher dose level. However, dosing may be resumed at a lower dose level.)

The study may be terminated early prior to full attainment of these criteria (eg, if just 1 subject experiences 1 of these events), if warranted by safety data from the other subjects dosed in the study to that point.

#### 6.3.2 Criteria for Premature Termination or Suspension of Investigational Sites

A study site may be terminated prematurely or suspended if the site (including the investigator) is found in significant violation of GCP, protocol, or contractual agreement, is unable to ensure adequate performance of the study, or as otherwise permitted by the contractual agreement.

# 6.3.3 Procedures for Premature Termination or Suspension of the Study or the Participation of Investigational Site

In the event that the sponsor, an independent ethics committee (IEC), or regulatory authority elects to terminate or suspend the study or the participation of an investigational site, a study-specific procedure for early termination or suspension will be provided by the sponsor; the procedure will be followed by applicable investigational sites during the course of termination or study suspension.

#### 7.0 SELECTION AND DISCONTINUATION/WITHDRAWAL OF SUBJECTS

All entry criteria, including test results, need to be confirmed at Screening and at Check-in (Day -1).

#### 7.1 Inclusion Criteria

Subject eligibility is determined according to the following criteria prior to entry into the study:

- 1. In the opinion of the investigator, the subject is capable of understanding and complying with protocol requirements.
- 2. The subject signs and dates a written, informed consent form and any required privacy authorization prior to the initiation of any study procedures including requesting that a subject fast for any laboratory evaluations.
- 3. The subject is a healthy adult male or female.
- 4. The subject is aged 18 to 55 years, inclusive at the time of consent.
- 5. The subject weighs at least 45 kg (99 lb) and has a body mass index (BMI) between 18.0 and 30.0 kg/m^2, inclusive at Screening.
- 6. A male subject who is nonsterilized\* and sexually active with a female partner of childbearing potential\* agrees to use adequate contraception\* from signing of informed consent throughout the duration of the study and for 90 days after 5 half-lives have elapsed since last dose of study drug. This should be interpreted as 90 days from the Follow-up Call/Visit unless data indicates otherwise.
- 7. A female subject of childbearing potential\* who is sexually active with a nonsterilized\* male partner agrees to routinely use highly effective contraception with low user dependency\* from signing of informed consent, throughout the duration of the study, and for 30 days after 5 half-lives have elapsed since the last dose of study drug. This should be interpreted as 30 days from the Follow-up Call/Visit unless data indicates otherwise.

\*Definitions and acceptable methods of contraception are defined in Section 9.1.10 Contraception and Pregnancy Avoidance Procedure and reporting responsibilities are defined in Section 9.1.11 Pregnancy.

#### 7.2 Exclusion Criteria

Any subject who meets any of the following criteria will not qualify for entry into the study:

- 1. Subject has received any investigational compound within 90 days prior to the first dose of study drug.
- 2. Subject is an immediate family member, study site employee, or is in a dependent relationship with a study site employee who is involved in the conduct of this study (eg, spouse, parent, child, sibling) or may consent under duress.

- 3. Subject has any clinically significant illness, such as cardiovascular, neurologic, pulmonary, hepatic, renal, metabolic, gastrointestinal, urologic, immunologic, endocrine, or psychiatric disease or disorder, or other abnormality, which may affect safety, increase risk of seizure or lower the seizure threshold, or potentially confound the study results. It is the responsibility of the investigator to assess the clinical significance; however, consultation with the Takeda Medical Monitor may be warranted.
- 4. Subject has a known hypersensitivity to any component of the formulation of TAK-653.
- 5. Subject has a positive urine/blood result for drugs of abuse (defined as any illicit drug use) at Screening or Check-in (Day -1).
- 6. Subject has a history of drug abuse (defined as any illicit drug use) or a history of alcohol abuse within 1 year prior to Screening or is unwilling to agree to abstain from alcohol and drugs throughout the study.
- 7. Subject has taken any excluded medication, supplements, or food products during the time periods listed in the Excluded Medications and Dietary Products table (listed in Table 7.a).
- 8. Subject is pregnant or lactating or intending to become pregnant before, during, or within 30 days after 5 half-lives have elapsed since the last dose of study drug (ie, 30 days from the Follow-up Call/Visit unless available data indicates otherwise); or intending to donate ova during such time period.
- 9. If male, subject intends to donate sperm during the course of this study or within 90 days after 5 half-lives have elapsed since the last dose of study drug. This should be interpreted as 90 days from the Follow-up Call/Visit unless data indicates otherwise.
- 10. Subject has had previous episodes of seizures or convulsion (lifetime), including absence seizure and febrile convulsion.
- 11. Subject or any immediate family member has a history of epilepsy (including febrile convulsions).
- 12. Subject has a history of neurological abnormalities including abnormal EEG at screening or brain injury including traumatic injury, perinatal cerebropathy and postnatal brain damage, blood-brain barrier abnormality, and angioma cavernous.
- 13. Subject has a history of cerebral arteriosclerosis.
- 14. Subject has a condition that can potentially reduce drug clearance (eg, renal or hepatic insufficiency).
- 15. Subject has current or recent (within 6 months) gastrointestinal disease that would be expected to influence the absorption of drugs (ie, a history of malabsorption, any surgical intervention known to impact absorption [eg, bariatric surgery or bowel resection], esophageal reflux, peptic ulcer disease, erosive esophagitis, or frequent [more than once per week] occurrence of heartburn).

- 16. Subject has a history of cancer, except basal cell carcinoma which has been in remission for at least 5 years prior to Check-in (Day 1).
- 17. Subject has a positive test result for hepatitis B surface antigen (HBsAg), hepatitis C virus (HCV) antibody, or a known history of human immunodeficiency virus (HIV) infection at Screening.
- 18. Subject has used nicotine-containing products (including but not limited to cigarettes, pipes, cigars, chewing tobacco, nicotine patch, or nicotine gum) within 28 days prior to Check-in Day -1. Cotinine test is positive at Screening or Check-in (Day -1).
- 19. Subject has poor peripheral venous access.
- 20. Subject has donated or lost 450 mL or more of his or her blood volume (including plasmapheresis), or had a transfusion of any blood product within 90 days prior to first dose of study drug.
- 21. Subject has a Screening or Check-in (Day -1) abnormal (clinically significant [CS]) ECG. Entry of any subject with an abnormal (not clinically significant [NCS]) ECG must be approved, and documented by signature of the principal investigator or medically qualified subinvestigator. In the case of a QTcF interval >450 ms or >480 ms (subjects with Bundle Branch Block) or PR outside the range of 120 to 220 ms, assessment may be repeated once for eligibility determination at the Screening Visit and/or Check-in (Day -1) Visit.
- 22. Subject has a supine blood pressure outside the ranges of ≥90 to ≤140 mm Hg for systolic and ≥50 to ≤90 mm Hg for diastolic. If out of range, assessment may be repeated once for eligibility determination at the Screening Visit and/or Check-in (Day -1).
- 23. Subject has a resting heart rate outside the range of 50 to 90 bpm (not on ECGs). If out of range, the assessment may be repeated once for eligibility determination at the Screening Visit and/or Check-in (Day -1).
- 24. Subject has abnormal Screening or Check-in (Day -1) laboratory values that suggest a clinically significant underlying disease or subject has the following lab abnormalities: ALT and/or AST >1.5 ULN.
- 25. Subject has a risk of suicide per the C-SSRS (a score of 4 or 5 on ideation or any suicidal behavior) or according to the investigator's clinical judgment, has made a suicide attempt in the previous 6 months, or has a history of deliberate self-harm in the past 6 months.

Additional exclusion criteria for collection in SRD/MRD Cohort 3:

- 26. The subject has had collected within 6 months prior to Check-in (Day -1).
- 27. The subject has a known hypersensitivity to the anesthetic or its derivatives used during collection or any medication used to prepare the area of lumbar puncture.
- 28. The subject has any skin condition, abnormality of the lumbar spine, medical or surgical condition that would preclude lumbar puncture (eg, coagulopathy, local or systemic infection,

left ventricular outflow obstruction, aortic stenosis, raised intracranial pressure, previous back surgery).

## 7.3 Excluded Medications, Dietary Products

Use of the agents in Table 7.a (prescription or nonprescription) is prohibited from the time points specified until subject is discharged from the unit.

**Table 7.a** Prohibited Medications and Dietary Products

28 days prior to Check-in (Day -1)	7 days prior to Check-in (Day -1)	72 hours prior to Check-in (Day -1)				
Prescription medications	OTC medications (a)	Products containing caffeine or xanthine				
Nutraceuticals (eg, St. John's wort, ginseng, kava kava, ginkgo biloba, Chinese herbs, and melatonin)	Vitamin supplements	poppy seeds				
Immunization/Vaccines (b)	Foods or beverages containing grapefruit or grapefruit juice, star fruit or star fruit juice, Seville-type (sour) oranges and marmalade, apple, orange, or pineapple juices, vegetables from the mustard green family (eg, kale, broccoli, watercress, collard greens, kohlrabi, Brussels sprouts, mustard), and charbroiled meats					
Nicotine-containing products	Alcohol containing products					
Intake of known OTC inhibitors/inducers of CYPs 3A4/5, 2C9, 2C19, 2D6, 1A2, 2B6, 2E1, and 2A6(c)						

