-----------	---------	--------	------	----------------

	TA	AK-653 Single Dose (b) (c)	
Cohort (a)	Planned	Actual	No. of Subjects
1	0.3 mg	0.3 mg	6 TAK-653 2 placebo
2	X mg	1.0 mg	6 TAK-653 2 placebo
3 (food-effect cohort) (d)	X mg	3.0 mg	6 TAK-653 2 placebo
4	X mg	5.0 mg	6 TAK-653 2 placebo
5	X mg	9.0 mg	6 TAK-653 2 placebo

- (a) Sentinel dosing will occur at the start of each Cohort in the SRD. After the investigator and sponsor review the 24-hour safety and tolerability data, the remaining subjects can be dosed in a staggered fashion (no more than 3 subjects at a time). A 24-hour gap will follow each subsequent administration to evaluate safety and tolerability data. (b) Dose escalation to Cohort 2 onward will be based on review of safety, tolerability, and available PK and PD data from the previous cohort(s).
- (c) TAK-653 or placebo will be administered orally to subjects after an overnight fast of at least 10 hours.
- (d) Subjects from SRD Cohort 3 (fasted conditions) will return to the clinic to receive the same dose of TAK-653 following a standard meal.

Subjects in the SRD Cohorts will be kept in the study unit for approximately 96 hours after dosing for safety and PK assessments before discharge. The total confinement period is 5 days. Subjects in Cohorts 1 to 5 will return to the clinic on Days 6 and 7 for additional PK collections. Subjects in Cohort 6 onward will return to the clinic on Days 6, 7, and 8 for additional PK collections. If the  $t_{1/2z}$  of TAK-653 for any cohort differs significantly from what was predicted, the duration of confinement may also be adjusted. Subjects in the food effect cohort will be confined twice for 5 days each for a total of 10 days. For SRD Cohort 6 onward,

Follow-up assessments for all subjects in the SRD study arm will occur on Day 14 (±2).

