# 9.1.15 Pharmacokinetic Sample Collection

9.1.15.1 Collection of Plasma and Urine for Pharmacokinetic Sampling

Blood and urine samples will be collected for the determination of concentrations of TAK-653, Urine samples will only be collected for the SRD/MRD Cohorts. The

sampling schedule may change based on emerging data but will not exceed the number of planned samples.

Serial blood and urine samples for determination of plasma and urinary concentrations of TAK-653 and its metabolites will be collected according to Table 9.c. The actual time of sample collection will be recorded on the source document and eCRF.

Table 9.c Collection of Blood and Urine Samples for Pharmacokinetic Analysis

Sample Type	Dosing Day	Time Postdose (hours)							
SRD (Cohorts	1-5)								
Plasma	1	Predose (within 15 minutes prior to dosing) and at 0.25, 0.5, 1, 1.5, 2, 3, 4, 6, 8, 10, 12, 16, 24, 36, 48, 72, 96, 120, and 144 hours postdose.							
SRD (Cohort 6	onward)								
Plasma	1	Predose (within 15 minutes prior to dosing) and at 0.25, 0.5, 1, 1.5, 2, 3, 4, 6, 8, 10, 12, 16, 24, 36, 48, 72, 96, 120, 144, and 168 hours postdose.							
SRD/MRD (Al	l cohorts)								
Plasma	1	Predose (within 15 minutes prior to dosing) and at 0.25, 0.5, 1, 1.5, 2, 3, 4, 6, 8, 10, 12, 16, 24, 36, 48, 72, 96, and 120 (a) hours postdose.							
Plasma	6	0.5, 1, 2, 4, 6, 8, 12, 16, and 24 (b) hours postdose.							
Plasma	12,14, 16	Predose (within 15 minutes of dosing) (and following collection procedure on Day 12, SRD/MRD Cohort 3 only).							
Plasma	18	Predose (within 15 minutes prior to dosing) and at 0.25, 0.5, 1, 1.5, 2, 3, 4, 6, 8, 10, 12, 16, and 24 hours postdose.							
Urine	1	Predose (-12 to 0 hours) and at (0 to 6), (6 to 12), (12 to 24), (24 to 48), and (48 to 72) hour intervals postdose.							
Urine	18	(0 to 6), (6 to 12), and (12 to 24) hour intervals postdose.							

a) The 120-hour sample must be collected before dosing on Day 6.

Blood samples (one 4-mL sample per scheduled time) for PK analysis will be collected into chilled Vacutainers containing anticoagulant (K2EDTA) according to the schedules in Appendix A, Appendix B, and Appendix C.

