#### **SRD**

The Screening/Baseline C-SSRS will be administered at Screening and Check-in (Day -1) and the Since Last Visit C-SSRS will be administered on discharge Day 5 and Study Exit Day 7 or Early Termination.

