7.7 Pharmacokinetic/Pharmacodynamic Analysis

7.7.1 Plasma Pharmacokinetic Concentrations

Collection of Blood Samples for PK Analysis (All SRD Cohorts)

| Sample Type | Dosing Day | Scheduled Time (hours) |
|-------------|------------|---|
| Plasma | 1 | Predose (within 15 minutes prior to dosing) and at 0.25, 0.5, 1, 1.5, 2, 3, 4, 6, 8, 10, 12, 16, 24, 36, 48, 72, 96, 120 and 144 hours postdose. Additional collection at 168 hours postdose for Cohort 6 onward. |

Collection of Blood Samples for PK Analysis (All SRD/MRD Cohorts)

| Sample | | |
|--------|------------|---|
| Туре | Dosing Day | Scheduled Time (hours) |
| Plasma | 1 | Predose (within 15 minutes prior to dosing) and at 0.25, 0.5, 1, 1.5, 2, 3, 4, 6, 8, 10, 12, 16, 24, 36, 48, 72, 96 and 120 (a) hours postdose. |
| Plasma | 6 | 0.5, 1, 2, 4, 6, 8, 12, 16, and 24 (b) hours postdose. |
| Plasma | 12, 14, 16 | Predose (within 15 minutes prior to dosing) (and following ^{CCI} collection procedure on Day 12 (SRD/MRD Cohort 3 only). |
| Plasma | 18 | Predose (within 15 minutes prior to dosing) and at 0.25, 0.5, 1, 1.5, 2, 3, 4, 6, 8, 10, 12, 16, and 24 hours postdose. |

(a) The 120-hour sample must be collected before dosing on Day 6.

(b) The 24-hour sample must be collected before dosing on Day 7.

For each part, the concentration of TAK-653, ^{CCI} in plasma will be summarized by TAK-653 dose level, Day, and period (fasted vs fed) over each scheduled sampling time using descriptive statistics (N, arithmetic mean, SD, median, minimum, and maximum). Individual plasma concentration data versus time will be presented in a data listing.

| TAK-653-1001 | Page 19 of 32 |
|---------------------------------|----------------|
| Statistical Analysis Plan Final | 22 August 2017 |

Blood samples for placebo will not be analyzed by the bioanalytical laboratory except for 2 samples per subject receiving placebo, 1 predose and the other around the expected time at which C_{max} occurred (as emerging from the actual measurement of the samples of the first dose group) to ensure from a safety perspective that no additional subjects were on active treatment. These data will be listed but not summarized.

For each part, individual concentrations of TAK-653, ^{CCI} in plasma will be plotted by actual time on linear and semilogarithmic scales. Plots of mean TAK-653, ^{CCI} plasma concentrations versus nominal time will also be provided on linear and semilogarithmic scales.

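### In the single-dose cohorts the Table 7.a prohibitions end at unit discharge (about 96 h), but PK samples continue at 120, 144 and, from Cohort 6, 168 h

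*Protocol*

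**What the plan says.** **End of the prohibition.** Protocol Section 7.3 states that use of the Table 7.a agents "is prohibited from the time points specified until subject is discharged from the unit". The table covers prescription and over-the-counter (OTC) medicines, vaccines, OTC inhibitors and inducers of several CYP enzymes, alcohol, and foods such as grapefruit, certain juices, mustard-family vegetables and charbroiled meat.

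**Discharge.** Under Section 6.1.1, SRD subjects "will be kept in the study unit for approximately 96 hours after dosing for safety and PK assessments before discharge". The SRD part of Section 9.1.21 treats discharge and study exit as separate events: the follow-up C-SSRS "will be administered on discharge Day 5 and Study Exit Day 7". Appendix B moves Study Exit to Day 8 from Cohort 6 onward.

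**Sampling after discharge.** Section 6.1.1 says "Subjects in Cohorts 1 to 5 will return to the clinic on Days 6 and 7 for additional PK collections" and "Subjects in Cohort 6 onward will return to the clinic on Days 6, 7, and 8 for additional PK collections". The Cohort 6 schedule in Table 9.c ends "24, 36, 48, 72, 96, 120, 144, and 168 hours postdose". SAP Section 7.7.1 agrees: "Additional collection at 168 hours postdose for Cohort 6 onward". Appendix H (Change 9) explains that the 168 h sample was added to describe the terminal half-life better at the higher single doses.

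**Other text that bears on Days 5 to 8.**
- Footnote (c) to Table 7.a, attached to the CYP row, has subjects consult the investigator before taking any medication. It gives no end date.
- Exclusion criterion 6 (Section 7.2) requires willingness to avoid alcohol and drugs for the whole study.
- Section 9.1.6 has concomitant medication asked about at each visit. Appendices A and B schedule this on Days 6, 7 and, where it applies, 8.
- Section 7.4 says subjects are confined for each treatment period, and Figure 6.a places Days 6 to 8 inside that period.

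**The concern.** The plan bars CYP-active products and foods for days or weeks before check-in, but the bar lifts before PK sampling is complete. The samples left outside it are the latest ones, which weigh most on the terminal slope.

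Protocol Section 9.1.16 defines AUC-infinity as AUClast plus the last concentration divided by lambda-z, so the late samples enter both terms. AUC-infinity on Day 1 is a secondary endpoint for all cohorts (Protocol Section 5.4.2, SAP Section 5.2). The AUCs, with Cmax, go into the power model and the fed/fasted comparison (SAP Section 7.7.2). If a subject took something after discharge that altered clearance, the half-life and the extrapolated area would partly reflect that exposure.

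**Working it through.** **1. Timeline.** Study day = 1 + hours/24, so 96 h is Day 5, 120 h Day 6, 144 h Day 7 and 168 h Day 8. This reproduces the visit days in Section 6.1.1.

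**2. Sample counts.** Table 9.c lists 19 postdose times for Cohorts 1 to 5 and 20 from Cohort 6. With the predose sample, 20 × 4 mL = 80 mL and 21 × 4 mL = 84 mL, matching the PK rows of Tables 9.f and 9.g. Samples after 96 h number 2 of 19 and 3 of 20.

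**3. Comparison with Part 2.** In SRD/MRD cohorts the last PK sample is 24 h after the Day 18 dose, and confinement lasts at least 72 h after that dose. The gap exists only in the SRD part.

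**4. What each safeguard covers after Day 5.**

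| Text | Medicines | Listed foods |
|---|---|---|
| Table 7.a prohibition | ended at discharge | ended at discharge |
| Footnote (c) | consult first; not a ban | not covered |
| Exclusion 6 | alcohol and drugs only | not covered |
| Section 9.1.6 | recorded | not recorded |

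**5. Share of AUC-infinity after 96 h.** For mono-exponential decline, share = exp(−ln2 × 96 / half-life). Section 6.2.1 predicts 10 h (rat) and 26 h (monkey). A longer value can be inferred from Section 6.2.2, which gives Day 18 means at 1 mg of 24.9 ng/mL (Cmax) and 503 h·ng/mL (AUC24). Then Cmax/Cav = 24.9/(503/24) = 1.19. In a one-compartment bolus model at steady state this ratio equals x/(1 − exp(−x)), with x = 24 × ln2 / half-life. Solving gives x ≈ 0.355 and a half-life of about 47 h.

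- 10 h: 0.1%
- 26 h: 7.7%
- 47 h: about 24%

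**6. Illustration of a possible shift.** Assume one subject's elimination rate is multiplied by f from 96 h on, with f between 0.5 and 2. If lambda-z comes from the last three samples (96–144 h, or 120–168 h from Cohort 6), the relative change in AUC-infinity is share × (1/f − 1).

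- 26 h: 0.077 × 1 = +8%, or 0.077 × (−0.5) = −4%.
- 47 h: 0.24 × 1 = +24%, or 0.24 × (−0.5) = −12%.

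A true half-life of 26 h would read 52 h or 13 h from those three samples, and about 35 h or 17 h from a fit over 48–144 h.

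**7. Effect on the fed/fasted ratio.** There are six active subjects in the food-effect cohort. If one were affected in one period, the geometric mean ratio would move by a factor of 1.077^(1/6) = 1.012 at 26 h, or 1.24^(1/6) = 1.037 at 47 h, for f = 0.5.

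**The case against.** The best counter-argument is that a reader might infer from Section 7.3 that everything in Table 7.a becomes freely allowed at Day 5 and that the late samples are unprotected. The documents do not support that. Footnote (c) has no stated end and covers every medication, use is recorded at each outpatient visit, and SAP Section 7.1.1 allows case-by-case decisions on noncompliant or incomplete data. This part of the objection stands: for medicines the gap is between a ban and a consultation rule. It does not reach the foods, which nothing restricts or records after discharge, and footnote (c) sits under a table whose own window has closed.

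A second inference would be that dose proportionality or the food effect is biased. The documents do not show this either. The rule is the same for every SRD cohort and both food-effect periods. A proportional shift common to all doses enters the power-model intercept, not the slope, and a common shift cancels in the paired comparison. What remains is added noise from sporadic intake, and step 7 shows that one affected profile moves the food-effect ratio only a little.

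Third, no visible passage says how TAK-653 clearance responds to CYP inhibition, induction or grapefruit. This also stands. The case for closing the gap rests on the plan's own decision to exclude these agents beforehand, not on a demonstrated interaction.

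Finally, Section 4.3 describes SRD Cohorts 1 to 5 as completed, and SAP Section 4.4 lists only one further SRD cohort. The reach of a change is therefore short.

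**Conclusion.** The timing gap is real, confined to the SRD part, and minor. After about 96 h the listed foods are unrestricted and medicines are no longer under a prohibition, while 2 of 19 or 3 of 20 postdose samples are still to come.

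The outputs exposed are lambda-z and the terminal half-life, which are calculated parameters and not listed secondary endpoints, and AUC-infinity, which is one. AUClast is slightly exposed. Cmax, tmax and AUC24 are unaffected.

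The exposed share of AUC-infinity runs from 0.1% to about 24% over half-lives of 10 to 47 h, assuming mono-exponential decline. The upper value also rests on a bolus model applied to ratios of reported means. It would be tempting to read these percentages as the size of an error. They are not: the shifts in step 6 require an assumed sustained halving or doubling of elimination in the affected subject. How many lambda-z points fall after discharge depends on the fit: 2 of 5 over 48–144 h, 3 of 6 over 48–168 h. The SAP defers further PK detail to the Clinical Pharmacology Analysis Plan.

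**What to change.** - For remaining SRD cohorts, end the PK-motivated restrictions in Table 7.a (the listed foods and the OTC CYP inhibitors/inducers) at the last PK sample, that is Study Exit, instead of at unit discharge. The rule for prescription medicines and vaccines after discharge is for the sponsor to settle.
- Reconcile Section 7.3 and footnote (c) with exclusion 6 (abstention for the whole study, although Table 7.a lists alcohol among items released at discharge), and Section 7.4 (confinement for the whole treatment period) with the outpatient visits in Section 6.1.1.
- For completed cohorts, flag recorded medication use after discharge when reporting lambda-z, the half-life and AUC-infinity. SAP Section 4.4 already shows an actual dose for SRD Cohort 6; if that cohort has been dosed and no further SRD cohort follows, this reporting step is what remains. Food intake cannot be recovered from the planned data.

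The protocol change is one phrase plus the reconciliation. After it, the number of PK samples outside the food and OTC inhibitor/inducer restrictions falls from 2 or 3 to 0. The cost to subjects is two more days of restrictions where sampling ends at 144 h, or three where it ends at 168 h, after they have left the unit.
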